### **New or Worsening Vertebral Fracture**

A new or worsening vertebral fracture is identified when there is  $\geq 1$  grade increase from the previous grade in any vertebra from T4 to L4.

### **Clinical Vertebral Fracture**

A clinical vertebral fracture is a new or worsening vertebral fracture assessed at either a scheduled or unscheduled visit and associated with any signs and/or symptoms of back pain indicative of a fracture, regardless of trauma severity or whether it is pathologic.

Signs and symptoms indicative of a vertebral fracture will be assessed using the Clinical Vertebral Fracture Back Pain eCRF. Data from this eCRF will be combined with the post-baseline lateral spine x-ray data from the central imaging

vendor by taking all back pain assessments prior to or on the date of the x-ray and the first eCRF record on or after the date of the x-ray and prior or on to the next x-ray date. If the x-ray date corresponds exactly with an eCRF record that indicates no back pain was present at the time of the x-ray, the subsequent back pain assessment will also be considered, so long as it is on or before the next x-ray. If any selected records indicate the subject experienced back pain consistent with a vertebral fracture, then the vertebral fracture will be considered as associated with signs and/or symptoms indicative of a vertebral fracture, and therefore a clinical vertebral fracture. If all selected records indicate that the subject did not experience back pain deemed consistent with a vertebral fracture by the investigator around the time of the fracture, then the fracture will not be considered a clinical vertebral fracture.

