#### **7.11 Clinical Fracture Recording**

##### **7.11.1 Suspected Clinical Vertebral Fractures (Primary Analysis Period)**

Information on suspected clinical vertebral fractures will be recorded until clinical fracture events (nonvertebral fracture or clinical vertebral fracture) have been confirmed for at least 330 subjects AND all subjects have had the opportunity to complete the Month 24 study visit. If, during the primary analysis period, a subject reports back pain that is considered by the investigator to be possibly due to a new or worsening vertebral fracture, a confirmatory lateral spine x-ray will be taken and the back pain (but not a vertebral fracture) will be recorded as an adverse event. The lateral spine x-rays as well as copies of other diagnostic images (computerized tomography or magnetic resonance imaging) and/or radiology report, surgical report, or discharge summary will be submitted to the central imaging vendor for confirmation of fracture (refer to [Section 7.14](#)). To confirm a clinical vertebral fracture, at least one new or one worsening (ie, change by at least 1 SQ grade) vertebral fracture have to be identified by the central imaging vendor on lateral spine x-rays. The central imaging vendor will inform the sites of any new or worsening vertebral fractures; however x-rays taken upon reporting of back pain may also be read locally if necessary to support subject medical care. Only clinical vertebral fractures confirmed by the central imaging vendor will be included for the statistical analysis.

Postfracture PRO/ClinRO assessments will be triggered by the investigator's decision to order the confirmatory lateral spine x-ray (refer to Section 7.12) after reporting of a suspected clinical vertebral fracture. However, only responses corresponding to clinical vertebral fractures confirmed by the central imaging vendor will be included for the statistical analysis.

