 11. Blood draws for BTMs must be obtained from subjects in fasting stage and before noon. Fasting stage is defined as overnight fasting. If overnight fasting is not feasible, at a minimum 8 hours is required.

12. SAE reporting to continue through 30 days after the last dose of IP.
13. Monthly contacts begin at M13. Contact will be initiated by a phone call. During the primary analysis period, if back pain is reported during the phone call, it will be recorded as an adverse event and the subject will be asked to complete an unscheduled follow-up clinic visit as soon as possible but no later than 21 days after reporting of the back pain for evaluation of a suspected clinical vertebral fracture.
14. Lateral spine x-ray will only be taken at the unscheduled follow-up clinic visit if the investigator considers the back pain previously reported during the monthly phone contact to be possibly due to a new or worsening vertebral fracture.
15. To facilitate subject scheduling, the Day 1/baseline lumbar spine DXA scan may be taken with the proximal femur DXA scan performed during screening. For Screening and Day 1 purposes, lateral spine x-rays and DXA scans of the lumbar spine and proximal femur taken up to 35 days prior to the beginning of the screening period may be used if all of the criteria outlined in [Section 7.2.1](#) are met.
16. In a subset of subjects.
17. To be processed and sent to the central laboratory during the primary analysis period; to be analyzed at local laboratories following the primary analysis period.
18. To be performed in the primary analysis period only.
19. To be performed at month 36 and then every 12 months thereafter during the primary analysis period only.
20. For subjects in the sub-study only.

Notes:

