## **4. Study Endpoints and Covariates**

### **4.1 Primary Endpoints**

*During the primary analysis period:*

- Subject incidence of clinical fracture (nonvertebral fracture and clinical vertebral fracture) at primary analysis
- Subject incidence of new vertebral fracture through Month 24

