### 6.4.4 Clinical Fracture

Clinical fractures include clinical vertebral as defined in [Section 6.4.2](#) and nonvertebral fractures (excluding skull, facial, mandible, cervical vertebrae, thoracic vertebrae, lumbar vertebrae, metacarpus, finger phalanges, and toe phalanges) as defined in [Section 6.4.3](#) that are associated with signs and/or symptoms indicative of a fracture. Nonvertebral fractures associated with high trauma severity or pathologic fractures will be excluded.

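### SAP 6.4.2 sets no lower time limit on the back-pain records that make a vertebral fracture clinical, so pain from an earlier x-ray interval can label a later silent fracture clinical (minor)

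*SAP*

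**What the plan says.** SAP 6.4.2 (Clinical Vertebral Fracture) joins the back-pain eCRF to the central x-ray readings.

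- Before the film, records are selected by "taking all back pain assessments prior to or on the date of the x-ray". No start date is given and there is no link to the previous film.
- After the film, only the first record counts, and only up to the next film. One more record is considered if the same-day record is negative.
- The positive test has no time condition: "If any selected records indicate the subject experienced back pain consistent with a vertebral fracture", the fracture is clinical.
- The only time wording is in the all-negative sentence, about pain "around the time of the fracture, then the fracture will not be considered a clinical vertebral fracture". Its length is not stated, and it does not restrict which records are selected.

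SAP 6.4.4 carries the definition forward ("Clinical fractures include clinical vertebral as defined in" Section 6.4.2) into a primary endpoint: "Subject incidence of clinical fracture (nonvertebral fracture and clinical vertebral fracture) at primary analysis". Sections 4.2, 4.4 and 6.4.6 carry it into clinical vertebral fracture through Months 12 and 24 and between them, and into major osteoporotic fracture.

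Protocol 7.11.1 says when pain leads to a film: if it is "considered by the investigator to be possibly due to a new or worsening vertebral fracture, a confirmatory lateral spine x-ray will be taken". Neither that section, Protocol 10.5.2.1, nor SAP 6.4.4 and 9.2.2 gives a look-back window.

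**The concern.** The rule has one open side. A woman can report suspicious back pain, have a film that shows nothing, recover, and later have a silent fracture found at a scheduled film. The old positive record is still among those selected, and it alone makes the new fracture clinical. That conflicts with the paragraph's own reference to pain near the time of the fracture. Two programmers could reasonably code it differently.

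Elsewhere the SAP does set such limits: 14 days for matching images to a reported nonvertebral fracture (6.4.3) and 45 days for the questionnaire at fracture report (6.1.1).

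At stake is which vertebral fractures enter one component of a primary endpoint. A window chosen after unblinding could look data-driven.

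**Working it through.** **The rule applied literally.** Take a constructed subject with a positive pain record on day 120, films without fracture on days 130 and 366, all later pain records negative, and a new fracture on the day 731 film. The SAP 6.4.2 selection includes day 120, so the fracture is clinical. If selection starts at the previous film (day 366), no positive record remains and it is not clinical.

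**Who can be affected.** Most endpoints count the first event. If the earlier pain belonged to a fracture already counted, a later label adds nothing. What remains is earlier pain without a confirmed fracture, no earlier qualifying event, negative records in the current interval, and then a grade increase. Year-one fractures mostly have no earlier post-baseline film, so exposure is mainly after Month 12.

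Month 12 to 24 is the exception. Its clock restarts at the open-label period (SAP 6.3), and its analysis set keeps everyone with one open-label dose (SAP 7.10). Year-one pain, even from a true year-one clinical fracture, can therefore label a year-two event.

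**The plan's own figures.** Pooled HR: exp(0.15 ln 0.50 + 0.85 ln 0.73) = 0.690, as stated. Events for 90% power at HR 0.70: 4 × (1.960 + 1.282)² / (ln 0.70)² = 330.4; at 330 events power is 90.0%. Both reproduce.

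**Inputs, per year (SAP 3.2.2 and 3.2.3).**

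- ALN: nonvertebral 4%; new vertebral 2.2%, of which 1/3 clinical (0.733%) and 2/3 silent (1.467%).
- Romosozumab/ALN: nonvertebral 4% × 0.55/0.75 = 2.933%; new vertebral 1.1%, split into 0.367% clinical and 0.733% silent.
- Clinical fracture: 4.733% and 3.300%, so HR = 0.697.
- Median events at primary analysis: 396.

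**Share of follow-up after year one.** Dropout of 10% then 8% gives 0.949 person-years in year one and 0.863 in year two. With uniform accrual over 34 months (assumed), follow-up runs from 24 to 58 months and averages 2.90 person-years. The share after year one is 1 − 0.949/2.90 = 0.673.

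**Effect on clinical fracture.** Let q be the assumed share of exposed silent new vertebral fractures that is relabelled, and e = 0.673q.

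- Events added = 396 × 2.2e / 8.033
- HR = (3.300 + 0.733e) / (4.733 + 1.467e)
- Power = Φ(½√D × |ln HR| − 1.96), with D = 396 plus the events added

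| q | Events added | HR | Power |
|---|---|---|---|
| 0 | 0 | 0.697 | 94.8% |
| 1% | 0.7 | 0.697 | 94.9% |
| 5% | 3.6 | 0.695 | 95.3% |
| 10% | 7.3 | 0.693 | 95.7% |

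A rough check without the accrual assumption: 396 / (2,000 × 8.033%) = 2.46 person-years per subject, so the share after year one is 1 − 0.949/2.46 = 0.61. Then q = 10% adds about 6.7 events, with HR 0.693.

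With no effect on either fracture type, numerator and denominator are equal and HR = 1 for every q.

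**Clinical vertebral endpoints.** Year two has 2,000 × 3.3% × 0.863 = 57.0 new vertebral fractures: 19.0 clinical and 38.0 silent. If 5% to 10% of the 38 were relabelled, 1.9 to 3.8 events would be added. That is 10% to 20% of 19.0 for Month 12 to 24, and 5% to 10% of 39.9 (2,000 × 1.1% × 1.812 person-years) through Month 24. The planned vertebral ratio of 0.50 does not change. Worsening fractures are left out because the plan gives no rate for them.

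**The case against.** The open look-back may be deliberate. The text takes all records before the film but only the first after it, which can be read as an inclusive choice. There is a clinical reason: SAP 13.2 lets grade 0 cover up to about 20% height loss, so pain, a normal early film and a grade change on the next film can be one true clinical fracture. This stands, and it is why the unbounded rule should stay as a sensitivity analysis. It does not explain the reference to pain near the time of the fracture.

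The size is also small and rests on an assumed share. The 10% to 20% for Month 12 to 24 is just twice that share, and the endpoint is exploratory, outside the testing sequence, and already flagged in SAP 10.5.3 as prone to bias. This too stands, and it limits the severity.

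A reader might infer three stronger points that the documents do not support:

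- **That the SAP contradicts the protocol.** Protocol 7.11.1 says "To confirm a clinical vertebral fracture, at least one new or one worsening" fracture must be identified centrally on lateral spine films. It does not say the pain-triggered film itself must show it.
- **That every silent fracture is exposed.** Applying 10% to year one as well would give 10.8 events and HR 0.691, but year-one fractures mostly have no earlier post-baseline film.
- **That events have been or will be mislabelled.** The code fragments are blacked out and may already use an interval. The back-pain eCRF is not in the documents, so it is an inference that pain judged possibly due to a fracture is stored as consistent with one.

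**Conclusion.** The gap is real and minor. As written, SAP 6.4.2 lets fracture-consistent pain from an earlier x-ray interval, with no confirmed fracture at the time, make a later silent fracture clinical. At an assumed 10% of silent new vertebral fractures after year one, with uniform accrual and plan dropout, clinical fracture gains about 7 events on 396 and the HR moves from 0.697 to about 0.693. The true share is unknown.

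A reader might take this as a threat to the primary result, but the documents do not support that. The rule is identical in both arms, every affected event is a centrally confirmed fracture, and type I error is not inflated when neither fracture type has an effect. New vertebral and nonvertebral fracture do not use the rule. Month 12 to 24 is the most exposed endpoint, because year-one pain can decide whether a year-two event counts.

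**What to change.** Before unblinding, amend SAP 6.4.2 as follows:

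- Limit the look-back to back-pain records dated on or after the previous evaluable lateral spine film (after baseline, for the first post-baseline film) and on or before the current film. An unreadable film should not reset the window.
- State how a record is assigned when it falls in both the forward window of one film and the look-back of the next, including a record dated on the earlier film's date.
- Use the same timing wording in the positive and negative sentences.
- Report the unbounded rule as a sensitivity analysis.

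The cost is a few lines of SAP text, a change to the derivation program, and one table. If the program already applies an interval, only the text changes. The bound may drop a few true clinical fractures whose pain came before a visible grade change; the sensitivity table shows how many. Power is not lost against the plan, which already counts only 1/3 of new vertebral fractures as clinical (94.8% at 396 events and HR 0.697).

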### **Multiple New or Worsening Vertebral Fractures**

A subject has multiple new or worsening vertebral fractures when there are  $\geq 2$  vertebrae from T4 to L4 with  $\geq 1$  grade increase from the previous grade. The multiple new or worsening vertebral fractures need not occur at the same visit.

#### **6.4.3 Nonvertebral Fracture (Osteoporotic)**

##### **Nonvertebral Fracture (Osteoporotic)**

Defined as a fracture present on a copy of radiographs or other diagnostic images such as computerized tomography (CT) or magnetic resonance imaging (MRI) confirming the fracture within 14 days of reported fracture image date on the eCRF (if day of the month is unknown, but month and year is known, then fracture images within the same month can be used to confirm), and/or documented in a copy of the radiology report, surgical report, or discharge summary, excluding skull, facial, mandible, cervical vertebrae, thoracic vertebrae, lumbar vertebrae, metacarpus, finger phalanges, and toe phalanges. In addition, fractures associated with high trauma severity or pathologic fractures will be excluded.

##### **Hip Fracture**

A subset of nonvertebral fractures including femoral neck, femur intertrochanter, femur subtrochanter, and "Other" location that are further specified as hip, pertrochanteric, or pertrochanteric femur.

##### **Distal Femur Fracture (ie, Femur Excluding Hip)**

A subset of nonvertebral fractures including femur distal and femur midshaft

##### **Wrist Fracture**

A subset of nonvertebral fractures including radius distal and ulna distal

### **Forearm Fracture**

A subset of nonvertebral fractures including radius, radius proximal, radius shaft, radius distal, ulna, ulna proximal, ulna shaft, and ulna distal

### **Rib Fracture**

A subset of nonvertebral fractures including ribs

### **Humerus Fracture**

A subset of nonvertebral fractures including humerus proximal, humerus shaft, and humerus distal

### **Proximal Humerus Fracture (ie, Humerus Excluding Elbow)**

A subset of nonvertebral fractures including humerus proximal and humerus shaft

### **Pelvic Fracture**

A subset of nonvertebral fractures including sacrum, acetabulum, ilium, ischium, and pubis

### **Leg Fracture**

A subset of nonvertebral fractures including femur midshaft, femur distal, patella, fibula, fibula proximal, fibula shaft, fibula distal, tibia, tibia proximal, tibia shaft, and tibia distal

### **Lower Leg With Ankle**

A subset of nonvertebral fractures including fibula, fibula proximal, fibula shaft, fibula distal, tibia, tibia proximal, tibia shaft, and tibia distal

### **Ankle Fracture**

A subset of nonvertebral fractures including fibula distal and tibia distal

### **Proximal Tibia Fracture (ie, Tibia Excluding Ankle)**

A subset of nonvertebral fractures including tibia proximal and tibia shaft

### **Foot Fracture**

A subset of nonvertebral fractures including metatarsus and tarsus

## Major Nonvertebral Fracture

A subset of nonvertebral fractures including pelvis, distal femur (ie, femur excluding hip), proximal tibia (ie, tibia excluding ankle), ribs, proximal humerus (ie, humerus excluding elbow), forearm, and hip

## Any Nonvertebral Fracture

Defined as any fractures recorded on the Clinical Non-vertebral Fracture Summary eCRF.

### 6.4.4 Clinical Fracture

Clinical fractures include clinical vertebral as defined in [Section 6.4.2](#) and nonvertebral fractures (excluding skull, facial, mandible, cervical vertebrae, thoracic vertebrae, lumbar vertebrae, metacarpus, finger phalanges, and toe phalanges) as defined in [Section 6.4.3](#) that are associated with signs and/or symptoms indicative of a fracture. Nonvertebral fractures associated with high trauma severity or pathologic fractures will be excluded.

### 6.4.5 All Fracture (Osteoporotic)

All osteoporotic fractures include any osteoporotic nonvertebral fractures that are not associated with high trauma severity or pathologic fractures and new or worsening vertebral fractures regardless of trauma severity or pathologic fractures.

### 6.4.6 Major Osteoporotic Fracture

Major osteoporotic fractures include hip, forearm, or humerus fractures that are not associated with a pathologic fracture regardless of trauma severity, and clinical vertebral fractures.

### 6.4.7 Historical Fracture

#### Any Historical Fracture

Any nonvertebral fractures recorded on the Subject Fracture History eCRF regardless of trauma severity or vertebral fracture based on baseline spinal radiograph.

#### Historical Osteoporotic Fracture

Any nonvertebral fracture recorded on the Subject Fracture History eCRF not including skull, facial bones, fingers, toes, spine and tailbone and not associated with known high trauma severity or pathologic fractures, or vertebral fracture based on baseline spinal radiograph

## Historical Nonvertebral Fracture

Fractures recorded on the Subject Fracture History eCRF not including skull, facial bones, fingers, toes, spine, and tailbone and not associated with known high trauma severity or pathologic fractures

## Historical Nonvertebral Fracture At or After Age 55

Historical nonvertebral fractures occurring at or after age 55

## Historical Major Nonvertebral Fracture

A subset of historical nonvertebral fractures including the following locations: pelvis (not hip), hip, lower leg (not knee or ankle), ribs, shoulder, forearm, and wrist and not associated with known high trauma severity or pathologic fractures

## Historical Fragility Fracture

Historical fragility fractures include moderate or severe vertebral prevalent fractures and nonvertebral fractures occurring at or after age 55.

## 6.5 PRO Measurements

### OPAQ-SV Physical Function Score

The physical function score is calculated by averaging nonmissing rating for 19 standardized items (question item numbers of 1 to 19;  $\geq 10$  items as nonmissing; otherwise set score to missing). The OPAQ-SV physical function score ranges from 0 to 100. A higher score represents better physical function. See [Section 13.3.1](#) for detailed scoring algorithm.

### OPAQ-SV Emotional Status Score

The emotional status score is calculated by averaging nonmissing rating of 11 standardized items (question item numbers of 20 to 24, and 29 to 34;  $\geq 6$  items as nonmissing; otherwise set score to missing). The OPAQ-SV emotional status score ranges from 0 to 100. A higher score represents better emotional status. See [Section 13.3.1](#) for detailed scoring algorithm.

### OPAQ-SV Back Pain Score

The score is calculated by averaging nonmissing rating of 4 standardized items (question item numbers of 25 to 28;  $\geq 2$  items as nonmissing; otherwise set score to missing). The maximum OPAQ-SV back pain score is 100. A higher score indicates less back pain. See [Section 13.3.1](#) for detailed scoring algorithm.

### EQ-5D-5L Health State Index Score

The EQ-5D-5L health state index score is calculated using the dimension scores from Question 35 a-e. The score ranges between  $-0.594$  and  $1.0$ , where

1 indicates full health; 0 indicates death. A score  $< 0$  indicates a state worse than death. See [Section 13.3.2](#) for detailed scoring algorithm.

## **EQ-5D-5L VAS Score**

The EQ-5D-5L VAS score ranges between 0 and 100 based on Question 36 (See [Section 13.3.2](#) for detailed question description). The score of 0 indicates “worst imaginable health state” and 100 for “best imaginable health state.”

## **7. Analysis Subsets**

### **7.1 Primary Efficacy Analysis Set For Vertebral Fractures**

This analysis set includes all randomized subjects who have a baseline and  $\geq 1$  post-baseline evaluation of vertebral fracture at or before the time point under consideration. This analysis set will additionally include subjects who have vertebrae with missing Genant semiquantitative scores at baseline and whose first post-baseline spinal radiograph shows no fracture on the same vertebrae because it can be inferred that the baseline scores would have also shown no fracture had they been available. Subjects in this subset will be analyzed according to their randomized treatment assignment, regardless of treatment received. This analysis set will be used as the primary analysis set for the following endpoints: new, new or worsening, and multiple new or worsening vertebral fractures.

### **7.2 Full Analysis Set**

This set includes all randomized subjects. Subjects in the full analysis set will be analyzed according to their randomized treatment assignment, regardless of treatment received. The full analysis set will be used as the primary analysis set for the following endpoints: nonvertebral fracture, clinical fracture, clinical vertebral fracture, all fracture, major nonvertebral fracture, major osteoporotic fracture, and hip fracture.

